Proprietary confidential information © 2021 Boehringer Ingelheim International GmbH or one or more of its affiliated companies

GPP	Generalised pustular psoriasis
HBV	Hepatitis B virus
HCV	Hepatitis C virus
HIV	Human Immunodeficiency Virus
HS	Hidradenitis suppurativa
IB	Investigator's brochure
IBD	Inflammatory bowel disease
ICF	Informed consent form
IEC	Independent Ethics Committee
IgE	Immunoglobulin E
IL36R	Interleukin 36 receptor
IQRM	Integrated Quality and Risk Management
IPD	Important protocol deviation
IRB	Institutional Review Board
ISF	Investigator site file
ITE	Indirect target engagement
IV	Intravenous
λ_z	Terminal rate constant in plasma
mAb	Monoclonal antibody
MRT	Mean residence time of the analyte in the body after intravenous bolus administration
PD	Pharmacodynamic(s)
PK	Pharmacokinetic(s)
PKS	Pharmacokinetic parameter analysis set
PPP	Palmoplantar pustulosis
ppPASI	Palmoplantar Pustular Psoriasis Area and Severity Index
PR	Pulse rate
QT	Time between start of the Q-wave and the end of the T-wave in an electrocardiogram
QTc	QT interval corrected for heart rate using the method of Fridericia (QTcF) or Bazett (QTcB)
REP	Residual Effect Period
RR	Respiratory Rate
SAE	Serious adverse event(s)
SC	Subcutaneous
$t_{1/2}$	Terminal half-life of the analyte in plasma
t_{max}	Time from dosing to maximum measured concentration of the analyte in plasma

Proprietary confidential information © 2021 Boehringer Ingelheim International GmbH or one or more of its affiliated companies

TS	Treated set
UC	Ulcerative colitis
V _{ss}	Volume of distribution at steady state after single intravenous administration
V _z	Volume of distribution during the terminal phase after intravascular administration
V _z /F	Apparent volume of distribution during the terminal phase after extravascular administration

1. INTRODUCTION

1.1 MEDICAL BACKGROUND

Spesolimab is a humanised antagonistic monoclonal IgG1 antibody that blocks human interleukin 36 receptor (IL36R) signaling. Binding of Spesolimab to IL36R is anticipated to prevent the subsequent activation of IL36R by cognate ligands (IL36 α , β and γ) and downstream activation of pro-inflammatory and pro-fibrotic pathways in inflammatory skin and bowel diseases such as generalised pustular psoriasis (GPP), palmoplantar pustulosis (PPP), atopic dermatitis (AtD), hidradenitis suppurativa (HS) and inflammatory bowel disease (IBD). Genetic human studies have established a strong link between IL36R signaling and skin inflammation, as demonstrated by the occurrence of GPP in patients with a loss-of-function mutation in IL36R α , the gene encoding the endogenous inhibitor of IL36R, which resulted in uncontrolled IL36R signaling [[R14-5158](#), [R15-1421](#)]. Mutations in other genes linked to the IL36 pathway such as CARD14 also lead to GPP [[R16-0929](#)]. IL36R signaling drives skin inflammation in several animal models, further supporting the strong link between IL36R biology and skin disorders based on human genetics [[R14-5158](#)].

IL36R is identified as a target for psoriasis based on (i) the abundant expression of all three stimulating ligands in human psoriatic lesional skin [[R14-4037](#)], (ii) IL36 α overexpression in murine keratinocytes inducing a psoriatic-like phenotype [[R15-1432](#)], (iii) IL36R KO mice protecting against Imiquimod-induced skin inflammation [[R15-1447](#)], and (iv) IL36R blockade ameliorating skin inflammation in a transplanted psoriatic skin model [[R15-1399](#)]. The link between IL36R-driven inflammation and epithelial inflammation has led to the hypothesis that IL36R signaling may play an important role in IBD. This hypothesis was tested using a suite of *in vitro* and *in vivo* assays. Immunostaining studies demonstrated that both IL36R and its ligands are expressed in intestinal biopsies taken from Crohn's disease (CD) patients. Human IL36 ligands enhance intestinal barrier permeability, a hallmark of IBD pathogenesis, using primary human intestinal epithelial cells co-cultured with intestinal myofibroblasts. The link between IL36R signaling and IBD was further strengthened by demonstrating that antagonist anti-mouse IL36R antibodies ameliorated intestinal inflammation in both acute chemically-induced and chronic T cell driven murine colitis models.

In addition, the therapeutic rational for an IL36R antagonist in IBD is based on the correlation of a set of IL36-induced genes upregulated in primary human intestinal myofibroblast, a disease relevant cell type, with gene signatures observed in ulcerative colitis (UC) and CD patients. Finally IL36R signaling in disease relevant cells such as intestinal myofibroblasts and macrophages induce both pro-inflammatory and tissue remodeling-related mediators (e.g. TGF- β , MMPs).

Altogether, these findings support a prominent role for IL36R in driving skin and intestinal inflammation and support anti-human IL36R antibody Spesolimab as a therapeutic agent for epithelial-mediated inflammatory diseases such as GPP, PPP, and IBD.

GPP is characterised by systemic inflammation of the skin and internal organs [[R15-1421](#); [R16-0933](#)]. Acute GPP is difficult to treat and no approved or standard of care therapy is available in the US or EU. Current treatment options aiming to control acute GPP and maintain

Proprietary confidential information © 2021 Boehringer Ingelheim International GmbH or one or more of its affiliated companies

response are cyclosporine, acitretin, and methotrexate [[R16-0933](#)]. Secukinumab, infliximab, brodalumab, and ixekizumab have been approved for GPP exclusively in Japan based on small local uncontrolled studies. To date, treatment is commonly not effective in suppressing acute flares during induction and recurrences emerge frequently.

PPP is a form of chronic PP characterised by sterile pustules limited to palms and soles [[R16-0927](#)]. Current, no approved or effective treatment is available.

Both UC and CD are characterised by abdominal pain, fever, bloody diarrhoea, and inflammatory lesions in the gastrointestinal mucosa. Current treatment options include aminosalicylates, glucocorticoid therapy, azathioprine, 6-mercaptopurine, and biologics (blocking TNF or integrin $\alpha 4\beta 7$). Treatment of CD and UC is associated with a significant number of patients with primary and secondary non-response. In addition, treatment may be limited due to safety and tolerability issues. Therefore, despite progress, there remains a significant unmet medical need for new treatment options with an improved safety and efficacy profile compared with the current therapeutic standard.

1.2 DRUG PROFILE

1.2.1 Nonclinical Pharmacology

Spesolimab is a humanised monoclonal antibody (mAb) of the IgG1 isotype that is directed against human IL36R. It is derived from mouse antibody 81B4 (BI 674308) cloned into a human IgG1 Kappa backbone. Spesolimab binds to human IL36R with a binding avidity of less than 1 pM. Spesolimab inhibits IL36 ligand-stimulated NF- κ B activation in transformed epithelial cells and in primary human keratinocytes, dermal fibroblasts and intestinal myofibroblasts with IC90 values in a consistent range of 0.7 to 3.7 nM. Spesolimab also inhibits IL8 release in dermal fibroblasts and keratinocytes and IFN γ secretion in human peripheral blood mononuclear cell) stimulated with IL36 α , IL36 β , or IL36 γ combined with IL12.

Mutations of two key residues (L234 and L235) to alanine were made to Spesolimab to abrogate FcR binding activity and function. Direct assessment of the impact of the mutations in the IgG1 FcR binding sites on both antibody-dependent cellular cytotoxicity (ADCC) and complement-dependent cytotoxicity (CDC) effector functions revealed that the mutations abrogate both ADCC and CDC effector functions and indicate that Spesolimab will be a non-depleting therapy in vivo.

1.2.2 Toxicology

Spesolimab does not bind to IL36R from common toxicology species. Therefore, meaningful toxicity studies cannot be performed in any animal species with Spesolimab. Hazard identification studies were performed in mice using a mouse specific anti-IL36R mAb (BI 674304), a mouse IgG2a mAb with rat variable regions. In a 13-week intravenous (IV) toxicity study of BI 674304 in mice, no adverse effects of IL36R antagonism were seen at a dose (50 mg/kg, twice weekly) that was 5-fold higher than the dose that was protective in an

Proprietary confidential information © 2021 Boehringer Ingelheim International GmbH or one or more of its affiliated companies

experimental mouse colonic inflammation model [[n00243876](#)]. In the 26-week toxicity study, male and female mice (20-30/sex/group at 0, 10 and 50 mg/kg/day) were administered BI 674304 twice weekly for 26 weeks by IV injection via the caudal vein [[n00257882](#)]. The *in vitro* cytokine release and tissue cross-reactivity assays demonstrate that the risk of transient cytokine release in humans is low and that, as expected, Spesolimab stains epithelium in a variety of tissues [[n00240832](#), [n00239291](#)]. There were no signs of local irritation after single, 1 mL injections of the subcutaneous (SC) formulation in rabbits [[n00248748](#)]. These preclinical data suggest Spesolimab may be safely administered to humans.

1.2.3 Nonclinical pharmacokinetics

Spesolimab has a very weak binding affinity to cynomolgus monkeys. Its pharmacokinetics (PK) characteristics in cynomolgus monkeys therefore addresses only the overall catabolic stability and FcRn recycling properties of the molecule, rather than full PK evaluation including possible specific target-mediated drug disposition. The PK of Spesolimab in cynomolgus monkeys were approximately dose linear following the IV administration of 0.3, 1.5, and 10 mg/kg of Spesolimab. The clearance, steady-state volume of distribution, and terminal half-life ($t_{1/2}$) for the three dose groups were similar ranging from 0.168-0.219 mL/h/kg, 65.2-83 mL/kg, and 284-349 h, respectively. The SC bioavailability was 62.6% [[n00243168](#)]. Anti-drug antibodies (ADA) were observed in both the 10 mg/kg IV and 1.5 mg/kg SC. dose groups, whereas the 0.3 and 1.5 mg/kg IV monkeys tested negative for ADA. In the two-week GLP toxicology study in CD-1 mice with Spesolimab, exposure increased proportionally from 10 to 50 mg/kg, and there was no apparent difference in Spesolimab serum exposure between male and female mice [[n00255537](#)].

1.2.4 Prediction of human pharmacokinetics

PK data suggest TMDD kinetics for Spesolimab [[c09985235](#)]. The saturation of the non-linear elimination pathway is likely to occur after 0.3 mg/kg and Spesolimab exhibits linear kinetics from the next dose-level onwards up to 10 mg/kg. Based on the PK results in GPP patients, the elimination $t_{1/2}$ of Spesolimab was observed to be approximately three weeks in patients who are ADA-negative and approximately one week in patients who tested ADA-positive [[c17444370](#)]. Steady state was not attained after four weekly doses in the multiple dosing groups and the accumulation ratios were similar for the various dose groups. Preliminary PK data suggest the exposure of a 300 mg SC dose of Spesolimab is similar when administered as a single 2 mL injection or two separate 1 mL injections, which potentially provides flexibility to dose 300 mg with either 1 mL or 2 mL pre-filled syringes in future trials.

Pharmacodynamic (PD) effects in this first-in-human (FIH) single-rising-dose trial [[c03361085](#)] were assessed by indirect target engagement (ITE) of IL36R by Spesolimab using an ex vivo whole blood stimulation assay. Preliminary analyses indicate that >99% peripheral IL36R receptor occupancy is achieved with doses ≥ 1 mg/kg from 30 minutes post infusion to ten week.

1.2.5 Clinical experience in humans

As of Sep 2020, six phase I trials and four phase II trials have been completed for Spesolimab, five phase I trials were conducted in healthy subjects, one phase I trial in GPP patients and four phase II trials in PPP, UC, AD patients.

The trial 1368-0001 was a single-rising-dose trial that assessed safety, tolerability, PK and PD of Spesolimab in healthy subjects [[c09985235](#)]. A total of 59 subjects received Spesolimab IV infusions from 0.001 mg/kg to 10 mg/kg while 19 subjects received placebo administration. Safety and tolerability of all tested IV doses were good. The most frequent treatment-emergent adverse events (AEs) were nasopharyngitis (Spesolimab: 20.7%; placebo: 15.0%), headache (Spesolimab: 8.6%; placebo: 15.0%), influenza-like illness (Spesolimab: 6.9%; placebo: 10.0%), and diarrhoea (Spesolimab: 3.4%; placebo: 10.0%). There were two AEs of moderate intensity (injection site haematoma, headache), all remaining AEs were of mild intensity. There were no serious adverse events (SAEs), no AEs that led to discontinuation of trial medication, no protocol-specified AEs of special interest and no other significant AEs. Furthermore, no relevant changes were observed in safety laboratory parameters, vital signs, and 12-lead ECGs. Importantly, there were no relevant differences in frequencies of subjects with treatment emergent AEs between the treatment groups, and no dose dependency was observed.

In the multiple-rising-dose trial 1368-0002, a total of 40 healthy male subjects were enrolled in five sequential groups comprising eight subjects per group. The trial consisted of four dose groups receiving rising multiple doses of 3 mg/kg, 6 mg/kg, 10 mg/kg or 20 mg/kg. In addition, one dose group received one single dose (20 mg/kg) only. Within each of the five dose groups, six subjects have been randomised to receive the active drug and two received placebo. In trial 1368.2, no dose dependency was observed for all AEs. The incidences of drug related AEs were balanced across treatment groups up to 10 mg/kg bw dose, while higher incidences were reported in the 20 mg/kg bw dose group. However, all AEs were of mild or moderate intensity.

Overall, multiple IV doses of 3 mg/kg, 6 mg/kg, and 10 mg/kg, as well as single and multiple doses of 20 mg/kg Spesolimab were found to be safe and well tolerated by the subjects in this trial. The incidences of drug-related AEs were balanced across treatment groups up to 10 mg/kg dose, while higher incidences were reported in the 20 mg/kg dose group. All AEs were of mild or moderate intensity. No dose-dependent AEs or other clinically relevant changes in safety laboratory parameters, vital signs, or 12-lead ECG were observed.

The relative bioavailability trial 1368-0003 explores PK as well as safety and tolerability of an SC formulation of Spesolimab at two different dose strengths of 150 mg (1 mL) and 300 mg (2 mL) in an open-label, sequential group design. In addition, the trial determines the relative bioavailability of the 300 mg SC dose (test group) compared to one single 300 mg IV dose of Spesolimab (reference group). The trial has been conducted in 36 healthy male and female subjects with 12 subjects per dose group. Local tolerability of the SC formulation was as well tolerated. Following an SC injection of 150 mg of Spesolimab, there were two cases of redness and one case of swelling at the injection site in 12 subjects. For the 300 mg SC dose there was one further report of redness in 12 subjects dosed. All local events were of mild intensity, occurred within 30 minutes after injection and completely resolved within 4 hours. There were no reports of injection site pain. The type, intensity and duration of systemic AEs were similar

Proprietary confidential information © 2021 Boehringer Ingelheim International GmbH or one or more of its affiliated companies

to what has been observed in the preceding single-rising dose / multiple rising dose studies 1368-0001 and 1368-0002. Most of the AEs were of mild intensity, there were no AEs considered to be dose limiting, and no SAEs.

In the single-rising-dosing trial in Japanese healthy subjects 1368-0009, 32 healthy Japanese male subjects were enrolled in four dose groups each comparing eight subjects per group. The trial consisted of three dose groups receiving single rising IV infusion doses of Spesolimab (300 mg, 600 mg, and 1200 mg) and one dose group receiving single SC doses of Spesolimab (300 mg). In each dose group, 6 subjects received Spesolimab and two subjects' placebo. A total of three of 18 subjects (16.7%) on IV doses of Spesolimab (one subject per IV dose level) were reported with an AE compared with two of eight subjects (25%) on placebo. No subject was reported with an AE following subcutaneous administration of spesolimab. AEs by preferred term reported on placebo were vomiting, chest comfort, and allergic rhinitis, while AEs reported on Spesolimab were upper respiratory infection (300 mg IV), contusion (600 mg IV), gastroenteritis (1200 mg IV), and temporomandibular joint syndrome (1200 mg IV). None of the observed AEs were judged by the investigator as related to the trial medication. SAEs, deaths, AEs of special interest (AESI) or other significant AEs (according to project definition) were not observed and no subject discontinued the trial due to an AE. The overall AE frequency following administration of single doses of 300 to 1200 mg IV or 300 mg SC. Spesolimab was comparable with placebo.

In 1368-0001 and 1368-0002 trials, TMDD-related PK profile was observed. The exposure showed dose-proportional profile from 0.05 mg/kg to 20 mg/kg in single IV infusion group. In 1368-0009 trial, the exposure was also dose proportional within the evaluated dose range (300 mg to 1200 mg). No severe AE was observed in the each trials.

The relative bioavailability trial 1368-0029 explored PK as well as safety and tolerability of an SC formulation of Spesolimab in four treatment groups [periumbilical injection of 300 mg SC given at one (x 2 mL) or two (2 x 1 mL) injection sites, periumbilical injection of 600 mg SC (2 x 2 mL) and 300 mg SC (1 x 2mL) given to the thigh]. A total of 48 subjects entered the trial and completed the planned observation time according to the clinical trial protocol. To sum up, Spesolimab was safe and well tolerated by the healthy subjects and no safety signal was identified in trial 1368-0029.

1.2.6 Residual Effect Period

The residual effect period (REP) of Spesolimab is 16 weeks. This is the period after the last dose with measurable drug levels and/or PD effects still likely to be present.

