3.2 DISCUSSION OF TRIAL DESIGN, INCLUDING THE CHOICE OF CONTROL GROUPS

The trial will be conducted in an open-label fashion. Blinding is not possible because the treatments are distinguishable. The open-label treatment is not expected to cause bias results, since the pharmacokinetic endpoints are derived from measurement of plasma concentrations of the analyte.

Proprietary confidential information © 2021 Boehringer Ingelheim International GmbH or one or more of its affiliated companies

For safety reasons, a time interval of at least two weeks (taking into consideration that the $t_{1/2}$ of Spesolimab is four weeks) will be maintained between the first drug administration in the previous dose group and the first drug administration of the subsequent dose group within each SC and IV dose groups.

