6. GENERAL ANALYSIS DEFINITIONS

6.1 TREATMENTS

For basic study information on investigational products, assignment of treatment sequences and selection of doses, please see CTP, Sections 3 and 4.

The study will be performed as a single dose, open-label non-randomized study in parallel-group design.

It is planned to include up to 60 healthy male and female subjects in the trial. The subjects will be assigned to 5 groups each consisting of 10 subjects with at least 3 subjects for each gender within each dose group. The cohorts within each SC and IV dose groups will be dosed sequentially.

For details of dosage and formulation see Table 6.1:1 below.

Table 6.1: 1 Labels for treatments for use in the CTR

Dose group	Treatment	Short label
1	A BI 655130, 450 mg, iv, once	Speso 450mg iv
2	B BI 655130, 900 mg, iv, once	Speso 900mg iv
3	C BI 655130, 1200 mg, iv, once	Speso 1200mg iv
4	D BI 655130, 300mg, sc, once	Speso 300mg sc
5	E BI 655130, 600mg, sc, once	Speso 600mg sc

The following separate study phases will be defined for the analyses of AEs:

- **Screening** (ranging from 0:00h (midnight) on day of informed consent until first administration time of study drug Spesolimab))
- **On treatment**
 - **BI treatment** (separately for each treatment, ranging from the time of first administration of Spesolimab / start of infusion of Spesolimab until time of administration + REP (defined as 16 weeks) / end of infusion + REP (defined as 16 weeks))
 - **Follow-up (F/U)** (ranging from administration / end of infusion of Spesolimab + REP until 0:00h (midnight) on the day after trial completion date))

The following AE displays will be provided in the report:

Section 15.3 and Appendix 16.1.13.1.8 (for ClinicalTrials.gov) of the CTR displays:

In these displays, the on treatment phase will be analysed (labelled with the name of the study treatment (short label)). Screening and Follow-up phases will not be included in this analysis.

The following totals will be provided in addition:

- a total over all on treatment phases included in this analysis ("Total") (Appendix 16.1.13.1.8 only)
- a total over all on treatment phases included in this analysis ("Total iv") (tables including iv treatment groups)
- a total over all on treatment phases included in this analysis ("Total sc") (tables including sc treatment groups)

Tables for ClinicalTrials.gov will be provided including both sc and iv groups.

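### The 16-week residual effect period looks too short by its own definition for the three IV groups and 600 mg SC, and it cuts the last nine weeks out of the adverse event tables

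*Protocol*

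**What the plan says.** Protocol 1.2.6 gives one value for all doses and both routes: "The residual effect period (REP) of Spesolimab is 16 weeks". The next sentence supplies the test that this value must meet: "This is the period after the last dose with measurable drug levels and/or PD effects still likely to be present". Either condition is enough. Neither document shows how 16 weeks was obtained.

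The protocol's other statements on duration are:

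- Section 1.2.4, from preliminary first-in-human data: ">99% peripheral IL36R receptor occupancy is achieved with doses" of at least 1 "mg/kg from 30 minutes post infusion to ten week".
- Section 1.2.4, half-life in GPP patients: "approximately three weeks in patients who are ADA-negative and approximately one week in patients who tested ADA-positive".
- Section 3.2, in the remark on dose spacing: the half-life "of Spesolimab is four weeks".

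The figure then drives the analysis. Protocol 7.3.4 assigns events after the residual effect period to follow-up. SAP 6.1 runs the on-treatment phase "until time of administration + REP (defined as 16 weeks", counted from the end of infusion for IV. It also excludes screening and follow-up from the Section 15.3 displays. SAP 7.8.1 uses these phases for the treatment-emergent analysis. Adverse events are collected to EoTrial on Day 176 (Protocol 5.2.6.2.1), and follow-up events appear in the listings (SAP 6.1).

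**The concern.** The secondary endpoints are the occurrence of treatment-emergent and of drug-related adverse events. The residual effect period sets where their tables stop. If the target is still blocked after week 16, an event that starts then is classed as falling after the drug effect and drops out of the summary tables, although it was collected. The doses here are far above the 1 mg/kg for which ten weeks of near-complete occupancy is reported, so a longer effect is to be expected. The same period also sets how long early withdrawals should be followed for adverse events (Protocol 3.3.4).

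**Working it through.** **The plan's own figure.** There is no formula to reproduce. Simple multiples of the stated half-lives give:

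- 4 × 4 weeks = 16 weeks
- 5 × 3 weeks = 15 weeks
- 5 × 4 weeks = 20 weeks

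Sixteen weeks equals five half-lives only if the half-life is 16/5 = 3.2 weeks. The fraction of drug left at week 16 is 2^(−16/h): 2.5% for h = 3 weeks and 6.25% for h = 4 weeks. The half-lives alone therefore do not contradict 16 weeks. A three-week half-life fits it, and a four-week half-life leaves it one half-life short of five.

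**Inputs for the occupancy check**

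- Reference level: the concentration that a 1 mg/kg dose has at week 10, still giving more than 99% occupancy (Protocol 1.2.4).
- Half-life h: 3 weeks (1.2.4, ADA-negative) or 4 weeks (3.2).
- Dose-proportional exposure: 0.05 to 20 mg/kg, and 300 to 1200 mg IV in the Japanese trial (1.2.5).
- SC relative bioavailability: 73.5% at 300 mg (1.3), assumed equal at 600 mg.
- Body weight: an assumption, 60 kg with a range of 45 to 85 kg. The protocol gives only lower weight limits and a BMI range.

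**Formulas.** With D the dose in mg/kg (SC doses multiplied by 0.735):

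- Level at week 16 relative to the reference = D × 2^(−6/h)
- Week at which the reference level is reached = 10 + h × log2(D)

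Example, 450 mg IV at 60 kg: D = 7.5 and log2(7.5) = 2.91. This gives 10 + 3 × 2.91 = 18.7 weeks, or 10 + 4 × 2.91 = 21.6 weeks.

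| Group | Relative level at week 16, 60 kg (h = 3 / 4) | Week reference level reached, 60 kg (h = 3 / 4) | Range over 45–85 kg and both h |
|---|---|---|---|
| 450 mg IV | 1.9 / 2.7 | 18.7 / 21.6 | 17.2–23.3 |
| 900 mg IV | 3.8 / 5.3 | 21.7 / 25.6 | 20.2–27.3 |
| 1200 mg IV | 5.0 / 7.1 | 23.0 / 27.3 | 21.5–28.9 |
| 600 mg SC | 1.8 / 2.6 | 18.6 / 21.5 | 17.1–23.2 |
| 300 mg SC | 0.92 / 1.30 | 15.6 / 17.5 | 14.1–19.2 |

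**Sensitivity to half-life.** The reference level is reached exactly at week 16 when h = 6 / log2(D). At 60 kg this is 2.06 weeks for 450 mg IV, 2.08 for 600 mg SC, 1.39 for 1200 mg IV and 3.20 for 300 mg SC. At 85 kg, 450 mg IV and 600 mg SC need 2.50 and 2.53 weeks. Both stated half-lives other than the ADA-positive one exceed these values in every group except 300 mg SC. With h = 1 week (ADA-positive), 1200 mg IV at 60 kg reaches the level at 10 + log2(20) = 14.3 weeks, inside 16.

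**Size of the window lost.** Sixteen weeks is 112 days, so the phase closes on Day 113. Day 176 is 175 days (25 weeks) after dosing. Then 175 − 112 = 63 days, and 63/175 = 36% of scheduled post-dose time lies in follow-up.

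**The case against.** The case for leaving 16 weeks alone has several parts.

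- **The basis may lie elsewhere.** Protocol 1.2.7 refers to the Investigator's Brochure for the drug profile. This stands: without a derivation, an assay limit or occupancy data beyond week 10, the figure cannot be shown to be wrong, only unsupported here and apparently short.
- **The occupancy data are preliminary and indirect.** They come from a trial that went to 10 mg/kg, while 900 and 1200 mg are 15 and 20 mg/kg at 60 kg. This stands as a caution. It is eased by the dose-proportional exposure reported to 20 mg/kg and from 300 to 1200 mg IV. Nor is it stated whether ten weeks ended the effect or only the observation; if only the observation, the projected times are too short.
- **Elimination is target-mediated at low levels.** The reference level equals about 0.10 to 0.18 mg/kg remaining, below the 0.3 mg/kg dose after which the non-linear pathway is said to saturate. This does not defeat the projection. A larger dose must first decline through the linear range to the 1 mg/kg level, taking h × log2(D) weeks, and only then begins approximately the ten-week course of a 1 mg/kg dose. The sum is the same formula.
- **ADA-positive subjects clear faster, and 300 mg SC straddles 16 weeks.** Both stand. The documents give no ADA incidence.

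A reader might also infer that PK sampling on Days 120, 148 and 176 shows that measurable drug is expected after the residual effect period. The documents do not support that: one schedule serves all doses, the same visits carry ADA samples, and results below quantification are provided for (Protocol 7.5.2).

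**Conclusion.** The concern holds for four of the five groups. For all IV doses and 600 mg SC, the protocol's own figures place the end of the reported occupancy level at about 17 to 29 weeks, so 16 weeks appears too short against the definition in 1.2.6. This rests on dose-proportional kinetics, log-linear decline with a half-life of three to four weeks, weights of 45 to 85 kg, equal SC bioavailability at both doses, and preliminary occupancy data. The three-week half-life comes from patients, and the four-week figure is given without a source.

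Three stronger readings might be inferred and are not supported. The first is that 16 weeks is wrong at every dose: no conflict is shown for 300 mg SC or for ADA-positive subjects, and the half-lives alone do not contradict it. The second is that late events are lost: they are collected to EoTrial and listed, and drug-relatedness remains the investigator's judgement. What is lost is their place in the summary tables for the secondary endpoints. The third is that Day 176 is the correct residual effect period: the projection for 1200 mg IV reaches 27.3 weeks at 60 kg with a four-week half-life, beyond the 25 weeks of observation.

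**What to change.** In SAP 6.1 and 7.8.1, tabulate treatment-emergent and drug-related adverse events from dosing to EoTrial (Day 176), either as the on-treatment phase or as an added table beside the 16-week one. State that Day 176 is the end of data collection and not an estimate of the residual effect period.

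In the protocol, the sponsor should reconcile the three- and four-week half-lives (1.2.4, 3.2) and the residual effect period (1.2.6) with the occupancy data, and give the basis for the figure. The clinical team should reconcile the other uses of 16 weeks in 3.3.2, 3.3.3 and 3.3.4. No replacement value is proposed here.

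The cost is wording and one set of tables; no new data are needed for subjects who complete. Redefining the on-treatment phase would also extend the laboratory and vital-sign tables, which SAP 6.1 ties to that phase; an added adverse event table would not. The downside is that background events from weeks 17 to 25 enter the counts of an uncontrolled trial, with a window longer by 63/112 = 56%. Showing both windows makes that visible.
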